
et al., 2003), the  $\rho$  for the CAPS was 0.05. Thus, use of  $\rho = 0.11$  in our power calculations is a conservative assumption. Larger values of the  $\rho$  can occur when the outcome measures (among patients) have a concrete connection to one another. In studies of physician behavior within a clinic, the  $\rho$  values are larger when the physician directly contributes to the assessment of the patient outcome measures. For example, Stedman et al. (2008) analyzed two such studies, one study of patients within selected clinics who were followed to determine if their clinic physician did or did not provide osteoporosis management, and a second study of patients within clinics to determine if physician education induced physicians to improve the quality of osteoporosis management. In each study the  $\rho = 0.12$ . The outcome measure for the patient was the level of disease management delivered by the physician, an outcome directly determined by the physician. In contrast, for our proposed study, the person who assesses patient outcomes should have little or no effect on the values of the patient measure outcome. In our study, the  $\rho$  captures a subtler effect, namely, potential assessor bias, a much smaller effect than the effect of physician practice patterns. With a proposed group size of 7, a maximum  $\rho$  of 0.11, and  $d = 0.50$ , we estimated a total  $n$  of 196, using  $p < .05$ . Although only two of 14 outcome variables in the pilot study exceeded  $\rho > .10$  (see [name] et al., 2009), we felt it was preferable to be conservative regarding  $\rho$  levels in our power computations. **Third**, in computation of sample size, we relied on .80 power level, as is customary in power calculations for RCTs. Using these parameters, the total desired  $n$  will be 196 ( $n = 98$  per condition); each treatment group will begin with 7 men. Thus, based on previous studies on Group CBT, as well as current data regarding ICC in the context of clinical trials, we have been appropriately conservative in our power calculations.

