In any RCT, missing data are inevitable. Analysis of only complete cases is biased; likewise, values not missing at random can bias the results. Thus, analyses that impute missing data must accordingly increase standard errors. In designing this trial, we have included features that are intended to minimize attrition, such as the presence of a project coordinator (who will make regular contact with each patient before and after treatment). Even with these features, we expect some missing data. The analytic plan is designed to make maximum use of the data. In particular, we will use multilevel latent growth modeling (estimator = maximum likelihood [ML]) using Mplus software. Within this approach, missing data are handled with direct ML (cf. Allison, 2001), retaining an effective  $N = 196$  for all analyses. In addition to fostering statistical power, modern missing data methods such as direct ML (and multiple imputation) provide accurate parameter estimates and standard errors (assuming that values are missing at random), unlike traditional methods such as restricting analyses to completers only or intent-to-treat (ITT) analyses. If we suspect that values are not missing at random, we will turn to methods discussed by Molenberghs and Kenward (2007), that are likelihood-based, intended for ITT studies, and tractable enough for standard statistical programs such as SAS. Potential bias due to attrition will be assessed by modeling 'missingness' patterns. In effect, these methods increase standard errors of the crucial study estimates thereby accounting for this source of uncertainty. If attrition occurs in a random manner (missing at random implies 'missingness' may depend on covariates but not on previous values of the outcome measure) then the mixed model produces unbiased estimates and conservative standard errors. Evaluations of potential bias, when attrition is not missing-at-random, requires cutting-edge statistical methodology (Daniels & Hogan, 2008). We will perform sensitivity analysis under various not-missing-at random assumptions following Daniels and Hogan's (2008) methodology.

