
***Hypothesis 2.*** Reductions in PTSD symptom severity will be maintained in the GCBT group at 12-month follow-up. Much as with Hypothesis 1, multilevel latent growth modeling will be used. In the analyses to examine Hypothesis 2, we will not include the treatment condition covariate but will include the site dummy code, to examine potential site differences. To test the prediction that the means of 6mos and 12mos do not differ, the slope factor loadings corresponding to these two time points will be constrained to equality and compared to the fit of a latent growth model where the 6 mo time point was freely estimated ( e.g., Baseline model:  $0^{* * 1}$ ; hypothesized model:  $0^{* * 1} 1$ ).

The **secondary aim** is to examine the generalizing effects of both GCBT and *SGP* on co-morbid conditions, distress and impairment. Because most trials in the PTSD literature do not include a thorough assessment of treatment generalization, it is unknown whether available treatments only address PTSD or whether gains generalize to related domains of functioning, including co-

morbid conditions such as depression, generalized anxiety, and alcohol use. Three hypotheses are proposed:

**Hypothesis 3.** For patients who are diagnosed with co-morbid Major Depressive Disorder (MDD), Generalized Anxiety Disorder (GAD), and/or Alcohol abuse prior to treatment, GCBT will produce significantly larger symptom reductions for these conditions, relative to SGP at post-treatment assessment and these generalized changes will show stability at 6 mo follow-up (FU). To test this hypothesis, we will use multi-level analysis, as discussed for Hypothesis 1. For continuous variables (BAI, BDI-II, SIP), we will use the same approach as described for Hypothesis 1. Although latent growth modeling can accommodate categorical outcomes (e.g., MDD+, MDD-) with an appropriate estimator (e.g., robust weighted least squares, maximum likelihood with numerical integration), there is concern about the estimation failure resulting from low cell frequencies, particularly at post-treatment and follow-up. In the event that cell frequencies are too low, we will augment the analyses from the continuous variables with more descriptively oriented statistics showing the rates of comorbidity decline at each assessment point as a function of treatment condition.

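### The claim of an effective N of 196 for all analyses is wrong, and the .80 power for the GCBT versus SGP contrast has no attrition allowance and is not met at the plan's own inputs

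*Combined protocol and SAP*

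**What the plan says.** - **Missing data (Analytic approach).** After listing features meant to limit attrition, the plan states: "Even with these features, we expect some missing data". It then says that direct ML handles the missing values, "retaining an effective" N of 196 for all analyses. The next paragraph includes every randomised case and plans to assess men who leave treatment early.
- **Sample size (the paragraph asking whether the RCT is adequately powered).** Inputs are d = .50 for GCBT versus SGP, ICC .11, group size 7 and p < .05, with sidedness not given. On power: "we relied on .80 power level, as is customary in power calculations for RCTs". The result is 196 men, 98 per arm, and "each treatment group will begin with 7 men". Section D.3 confirms that 196 is the number who start; the step from 280 to 196 is screening loss. No allowance is made for missing outcomes.
- **Hypotheses 2 and 5 (D.7.a).** Both concern maintenance of gains in the GCBT group at 12 months. For Hypothesis 2, "we will not include the treatment condition covariate but will include the site dummy code". Hypothesis 5 follows the same approach.
- **Hypothesis 3 (D.7.a).** The population is restricted: "For patients who are diagnosed with co-morbid Major Depressive Disorder (MDD), Generalized Anxiety Disorder (GAD), and/or Alcohol abuse prior to treatment". No subgroup size is given.
- **E.1.** Assessments judged invalid, and statistical outliers, may be excluded from analysis.

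**The concern.** An effective sample size describes information, not how many records enter a likelihood. The plan expects missing outcomes and also claims that the full 196 is retained, and both cannot be true. The words covering all analyses also extend the claim to hypotheses whose populations are smaller than 196 from the outset.

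Two things are at stake. The Hypothesis 1 power statement assumes complete data in full groups of 7, so its margin against attrition is undisclosed. And a reader could take a null result on Hypothesis 3 as resting on 196 men when it rests on a subgroup of unstated size.

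**Working it through.** **1. The plan's own figure.** Inputs from the power paragraph: d = .50, ICC .11, m = 7, power .80, alpha .05 (two-sided assumed).

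- Per arm without clustering: 2 × (1.960 + 0.842)² / 0.50² = 62.8.
- Design effect: 1 + (7 − 1) × .11 = 1.66.
- Per arm with clustering: 62.8 × 1.66 = 104.2, or 208.5 in total. Rounding up to 15 groups of 7 per arm gives 210.

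So 196 is not reproduced. A one-sided test would need 166, so it does not explain the figure. ICCs of .08 or .09 do give 196 after rounding up to 14 groups per arm; .11 does not.

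**2. Power at 196 with complete data.** The noncentrality is d × √(n / (2 × DE)) = .50 × √(98 / 3.32) = 2.717. Normal approximation: Φ(2.717 − 1.960) = 77.5%. With a t reference on 28 − 2 = 26 df it is 74.4%.

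**3. Power with missing endpoint data.** The plan gives no rate, so 10–30% is an assumed range. For missing fraction a, n = 98(1 − a), m = 7(1 − a) and DE = 1 + (m − 1) × ICC. There is no recovery from other visits or from baseline.

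| Missing | n per arm | DE (ICC .11) | Power, z | Power, t (26 df) |
|---|---|---|---|---|
| 0% | 98 | 1.660 | 77.5% | 74.4% |
| 10% | 88.2 | 1.583 | 75.1% | 71.9% |
| 20% | 78.4 | 1.506 | 72.3% | 69.0% |
| 30% | 68.6 | 1.429 | 68.8% | 65.5% |

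The loss due to missingness alone is therefore about 2 to 9 points (77.5 − 75.1 = 2.4; 77.5 − 68.8 = 8.7). The remaining 2.5 points below .80 are present with no loss at all.

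**4. Sensitivity to the ICC.** The power paragraph reports CAPS ICCs of .07 (motor-vehicle-accident pilot) and .05 (earlier VA cooperative group-therapy study). With 10% missing, power is 80.9% and 83.9% (z), or 77.9% and 81.1% (t). With 20% missing it is 77.7% and 80.6% (z).

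**5. What direct ML can recover.** Ignoring clustering, if an endpoint with fraction a missing correlates r with a fully observed visit, the variance of its ML mean is inflated by 1 + [a/(1 − a)] × (1 − r²). For a = .20 and assumed r of .3 to .7, the inflation is 1.2275 to 1.1275, equivalent to 196/1.2275 = 160 to 196/1.1275 = 174 complete cases. Recovery is partial.

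**6. Populations below 196 by definition.**

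- Hypotheses 2 and 5: 98 men if fitted in the GCBT arm alone, about 98/1.66 = 59 independent cases at ICC .11.
- Hypothesis 3: section C.2 reports that 83% of the pilot veterans had a comorbid disorder of any kind. Applied here, .83 × 196 ≈ 163 men, and no single disorder can exceed that. Borrowing d = .50, with n = 98f and m = 7f for subgroup share f, power (z) at ICC .11 is 73% at 83%, 59% at an assumed 50% and 44% at an assumed 30%. At 83% and the pilot BDI-II ICC of .03 it is about 85%. The spread shows that the documents do not settle the figure.

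**The case against.** The strongest defence is that the phrase is loose wording. In context it contrasts direct ML with completer-only deletion. The same paragraph says that analyses imputing data must widen standard errors, and D.7.a openly restricts Hypothesis 3. On this view nobody is misled. What stands is that the plan does not say in so many words that dropout costs no power, so a reader who infers that goes beyond the text. But the acknowledgement of wider standard errors contradicts a fully retained effective N, so the phrase is still wrong.

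A second line is that the power loss is exaggerated. Part of this stands. The CAPS ICCs actually reported are below .11; repeated measures and baseline adjustment could add power; and men who leave treatment are still to be assessed, so treatment dropout is not the same as a missing outcome. The only veteran pilot rate is 1 of 12 missing at post-treatment; at 8.3% the figure in step 2 falls only from 77.5% to about 75.6%. Against this, the plan chose .11, calls it conservative, and takes no credit for repeated measures or baseline in its calculation.

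Third, the plan does not say that the SGP arm is dropped for Hypothesis 2. That also stands: 98 is an inference from the hypothesis wording and the omitted treatment covariate.

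**Conclusion.** The statement about an effective N of 196 is wrong as written and should be corrected. Separately, the .80 power for the GCBT versus SGP contrast is not met at the plan's stated d, ICC and group size. It is about 77.5% (z) or 74% (t, 26 df) with complete data, because about 210 men are needed, and about 75%, 72% and 69% (z) at 10%, 20% and 30% missing. These figures assume a two-sided test, group sizes shrinking in proportion to the missing fraction, and no recovery from other visits or baseline.

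Three stronger readings go too far. A reader might infer that stated power and precision fail for every hypothesis. No precision is stated anywhere, and .80 is stated only for the between-arm contrast; for Hypotheses 2, 3 and 5 the gap is that power is not addressed. A reader might blame the whole shortfall on missing data, but part of it exists with none missing. And a reader might conclude that the trial must fall below .80 for CAPS. At the reported ICCs of .05 to .07, 10% missing still leaves about 81–84% by the normal approximation.

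**What to change.** 1. Replace the phrase with wording such as: *all randomised men, apart from exclusions under E.1, contribute to the two-arm models for Hypotheses 1 and 4; information falls with missing outcomes.*
2. Restate Hypothesis 1 power at d = .50 and ICC .11 as about 77.5% (z; 74% by t) with no loss, and about 69–75% (z) at 10–30% missing. Label the missing rates as assumptions, and show the ICC .05 and .07 results beside them.
3. Specify the analysis set for Hypotheses 2 and 5 (98 men if GCBT only) and the expected subgroup size for Hypothesis 3, and say that no power is claimed for these.

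The cost is text only. No extra enrolment is proposed; the one downside is a less favourable stated power.

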### **Outcome variables:**

**Measures of PTSD symptoms** will include the Clinician Administered PTSD Scale - 5 (CAPS -5) and the Posttraumatic Check List - 5 (PCL-S-5). The CAPS-5 has been discussed in Section D1 (Study Participants). The CAPS-5 will serve as the primary outcome measure for PTSD. Both measures derived from the CAPS-5 will be used (presence/absence of PTSD diagnosis and overall PTSD severity score

Other measures include:

- The PTSD Checklist-5 (PCL-5; Weathers, Litz, Huska, & Keane, 1994) is self-report measure of PTSD, that corresponds to the DSM-5 symptoms of PTSD. Like the CAPS, the PCL can be scored to yield an overall severity score (total score). Psychometric properties of the prior PCL are sound (Weathers et al., 1994). The proposed project will use the PCL-S-5, a version that requests individuals to state the index event for which they are rating symptoms. In addition to the assessment map provided in Table 4, the PCL5 will be administered weekly during treatment, in order to track participant risk. Greater details about how the PCL data will be used to assure participant safety can be found in Section E.2.

**Measures of distress and impairment** Three subscales of the Medical Outcomes Study Short-Form Health Survey (SF-36; Ware & Sherbourne, 1992) will be used to index objective role functioning/impairment. These scales are the Role Limitations due to Physical Problems (role-physical), Role Limitations due to Emotional Problems (role-emotional), and Social Functioning subscales which appear to be minimally confounded with psychopathology. All three of these subscales have shown factorial validity and discriminative validity (Ware & Sherbourne, 1992).

- **Health care utilization** will be examined as an exploratory aim to investigate the effect of PTSD group treatment on health care utilization. This measure will be evaluated via record tracking. Veterans may obtain medical care within or outside of the VA system. When men initially enroll in the project, we will ask the names of their medical providers. Physician records in the VA system can be electronically accessed using the CPRS system. For physicians outside of the VA system, we will seek a signed release of information, which will permit contact to track the number of visits. The Project Coordinator will keep monthly records of the number of medical visits (excluding wellness visits) for each participant.

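### Missing at random is defined too narrowly, and the term triggers an unspecified move to other methods; correct the definition and fix direct ML as primary

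*Combined protocol and SAP*

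**What the plan says.** The Analytic approach text that precedes D.7.a sets out the missing-data plan in one paragraph.

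- **Method.** The analysis is "multilevel latent growth modeling (estimator = maximum likelihood [ML]) using Mplus software", with missing values handled by direct ML. Direct ML is said to "provide accurate parameter estimates and standard errors (assuming that values are missing at random"). Analysis of complete cases only is called biased.
- **Trigger.** "If we suspect that values are not missing at random, we will turn to methods" taken from a cited textbook.
- **Definition.** Later in the same paragraph, MAR is said to imply that missingness "may depend on covariates but not on previous values of the outcome measure". When this holds, the mixed model is said to be unbiased.
- **Other steps.** Missingness patterns will be modelled, and sensitivity analyses under not-at-random assumptions are planned without any condition.

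Elsewhere, D.7.a specifies the multilevel latent growth model for Hypothesis 1, with CAPS total as the dependent variable and the PCL modelled separately. Section E.2 provides for removing participants whose condition deteriorates. The Analytic approach text also says that men who leave treatment voluntarily will still be approached for the mid, post and follow-up assessments. No other section defines MAR or says what would count as suspecting its failure.

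**The concern.** The definition describes a narrower condition than MAR, and the term does work in the plan: it separates the case in which direct ML is relied on from the case in which the team goes to other methods. Missing CAPS scores related to an earlier observed CAPS score fall on the wrong side of the plan's line, although direct ML handles them. Some symptom-related missingness is foreseeable, because Section E.2 removes men who deteriorate.

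Two things are at stake. The plan misstates what its main analysis assumes. And, because the trigger is an uncriterioned judgement made once data are in hand, the main method could be changed needlessly after the data are seen, to one resting on assumptions that the data cannot check.

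**Working it through.** **1. The definitions side by side.** Let R be the missingness pattern, X the covariates, Yobs and Ymis the observed and missing outcomes.

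- Covariate-dependent MCAR: P(R | X, Yobs, Ymis) = P(R | X).
- MAR: P(R | X, Yobs, Ymis) = P(R | X, Yobs).
- Not at random: R still depends on Ymis given X and Yobs.

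The plan allows X and bars earlier outcome values, which is the first line.

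**2. Why direct ML needs only the second line.** Under MAR the likelihood factors as f(Yobs | X, θ) × P(R | X, Yobs, ψ). With θ and ψ distinct, the second factor carries no information on θ, so ML on the observed outcomes is valid if the outcome model is right.

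**3. Consistency with the plan's own argument.** If missingness depended only on covariates in the model, a covariate-adjusted completer analysis would be unbiased too. The advantage in bias that the plan claims for direct ML over completer analysis comes from the case that its definition excludes.

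**4. Simulation of ML validity.** From the documents: 196 men, 14 groups of 7 per arm, ICC 0.11, d = 0.50. Assumed: within-person correlation 0.6, baseline dropout 15–35%, odds ratio (OR) for dropout 1 to 3 per SD, three occasions (pre, mid, post). There were 3,000 replicates. ML for monotone multivariate-normal data stood in for the growth model. The check was a two-sided 5% test of the mid score in a logistic regression of dropout on arm and mid score (800 replicates). Bias is in SD units, with Monte Carlo SE 0.003–0.004 for ML.

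| Dropout before post | ML bias | Complete-case bias | Check significant |
|---|---|---|---|
| Unrelated to score | -0.005 to -0.001 | -0.004 to 0.001 | 4–6% |
| Observed mid score, OR 1.5 | -0.003 to 0.002 | 0.003 to 0.005 | 53–74% |
| Observed mid score, OR 2 | 0.000 to 0.003 | 0.009 to 0.014 | 92–99% |
| Observed mid score, OR 3 | -0.005 to 0.002 | 0.021 to 0.025 | 100% |
| Mid score, one arm only, OR 2 (25%) | 0.001 | -0.101 | 49% |
| Mid score, one arm only, OR 3 (25%) | -0.001 | -0.154 | 79% |
| Unseen post score, one arm only, OR 2 (25%) | -0.084 | -0.150 | 20% |
| Unseen post score, one arm only, OR 3 (25%) | -0.123 | -0.218 | 36% |

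In every row but the last two, ML is essentially unbiased. In the last two, where it is biased, the check is usually silent. Dependence on earlier outcomes is thus a poor marker of when direct ML fails.

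**5. A simpler version that can be checked by hand.** Assume 20% dropout and one standardised predictor. The SE of the log odds ratio is about 1/√(196 × 0.20 × 0.80) = 1/√31.36 = 1/5.6. Then z = 5.6 × ln(OR), and power ≈ Φ(z − 1.96).

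- OR 1.3: z = 5.6 × 0.262 = 1.47; power 31%.
- OR 1.5: z = 5.6 × 0.405 = 2.27; power 62%.
- OR 2.0: z = 5.6 × 0.693 = 3.88; power 97%.

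Two simulation runs of 1,000 replicates gave 27–29%, 59–62% and 96%. At 10% dropout the rates were 21%, 38% and 77%; at 30%, 38%, 70% and 99%.

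**The case against.** The best case on the other side accepts the error in the definition and disputes its consequences. Most of it stands.

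- **Replacement is not stated.** A reader might infer that the primary analysis will be swapped. The text does not say so: D.7.a sets the growth model for Hypothesis 1 without condition, not-at-random sensitivity analyses are planned in any event, and the other methods may be meant as a supplement. What remains is that the plan leaves this open.
- **The percentages are not the chance of a switch in this trial.** The plan contains no missingness regression and no 5% threshold. The figures are the power of one possible check under assumed dropout and odds ratios.
- **The frequency of the pattern is unknown.** A reader might infer that symptom-related dropout is the commonest kind. The documents give no attrition patterns, and voluntary leavers are to be followed up, so leaving treatment is not the same as a missing CAPS score. The removal rule makes such missingness foreseeable, no more.
- **The PCL is a different matter.** It is tempting to say that dropout after high weekly PCL-5 scores is equally harmless. The PCL is not the outcome in the CAPS model, so the plan's definition does not clearly exclude it, and dropout driven by scores left out of that model is not clearly ignorable. A simulation with assumed correlations gave ML bias of -0.05 SD (OR 2) and -0.07 SD (OR 3) when this happened in one arm only, and about zero when both arms shared the mechanism. Suspecting a departure from MAR is therefore not always a false alarm.

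**Conclusion.** The concern holds in a limited form. The plan's only definition of MAR is wrong, and that term governs a move to other methods for which no criterion or status is given. Read literally, missing CAPS scores related to earlier observed CAPS scores would meet the trigger although direct ML remains valid, so a needless change of the main method after the data are seen is possible.

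Its probability cannot be derived from the documents; the flag rates above show direction and rough size only. Nor do the documents support a claim that the primary model is biased: the estimator is appropriate under MAR correctly defined, with ML bias within 0.005 SD in all simulated cases of dropout driven by the observed outcome. The definitional error is certain; its effect on the conduct of the analysis depends on how the team would apply an open rule. The text should be corrected.

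**What to change.** Two changes to the Analytic approach text:

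1. Replace the definition with: *MAR means missingness may depend on observed data in the model, including covariates and previously observed outcome values, but not on unobserved values given these.*
2. State that direct ML is the primary analysis whatever missingness mechanism is suspected, and that all not-at-random models are sensitivity analyses that supplement it and do not replace it.

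The cost is wording only: no new data and no change of estimator. Using PCL-5 scores as auxiliary variables is optional and not part of this correction. Entering up to 14 weekly scores in a two-level model with 28 groups would be debatable; if the team wants to use them, a summary such as the last observed score, in a sensitivity analysis, would be more manageable.
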